Study Title: A PILOT STUDY TO EVALUATE THE EFFICACY OF VACUUM-ASSISTED DRESSINGS (V-AD) IN THE MANAGEMENT OF OPEN CHEST WOUNDS

Version date: 5/7/2018

NCT02803164

Protocol V1.7, 5/7/2018

A. GENERAL STUDY INFORMATION

A.1. Study Title: A PILOT STUDY TO EVALUATE THE EFFICACY OF VACUUM-ASSISTED DRESSINGS (V-AD) IN THE MANAGEMENT OF OPEN CHEST WOUNDS

A.2. Investigators

A.2.1. Principal Investigator: [name]

Coordinator: [name]

Statistician: [name], MS

A.2.2. Co-Principal Investigator: [name], MPH

Coordinator: [name]

B. STUDY PURPOSE

B.1. Hypothesis: Vacuum-assisted dressings (V-AD) are effective in treating patients with open chest wounds (OCW) and will decrease the time-to-closure of such wounds when compared to a historical cohort of patients managed by traditional wound care management.

B.2. Aims:

- Obtain definitive evidence for the effectiveness of V-AD in the management of OCW through a well-designed prospective pilot study conducted at 2 campuses of Mayo Clinic (Florida and Rochester).
- b. Compare the rate of healing (time-to closure) of OCW in patients treated with V-AD to a historical cohort of patients with OCW treated at Mayo Clinic without V-AD. Time to wound closure further being defined as the total approximation of the wound edges to close the defect.
- c. Determine if treatment with V-AD reduces the need for additional procedures to close wounds, such as muscle flaps.

C. BACKGROUND

Pleural space infections (empyemas) can occur either spontaneously or in the postoperative setting after any type of thoracic or abdominal surgery. The management of infected thoracic cavities has been one of the most frustrating problems encountered by thoracic surgeons. Post-operative infections occurring in the presence of concomitant bronchopleural fistulas (BPF) increase the complexity of treatment even more. While in many cases of empyema temporary drainage and antibiotic therapy will help resolve the infection, in others a more permanent drainage method such as an open chest window (a.k.a Eloesser window) may be required. The resulting open chest wounds

require frequent debridement and daily dressing changes for unspecified duration, imposing a tremendous financial and mental burden on the caretakers and patients. In addition, access into the chest cavity during dressing changes can be difficult and painful, which can result in small pockets of undrained infection.

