Due to chronic infection and the large space that exists, these wounds may take months or even years to close by secondary intention. In order to expedite the closure of the wound, additional procedures such as modified Clagett procedure (advancement of muscle flap) or thoracoplasty (collapse therapy) are often performed once the infection subsides. These operations can be quite morbid and are not always successful in obliterating the space in the chest cavity.

The technical and psychosocial challenges encountered in managing these chronic wounds have led to the more recent use of V-AD as an alternative way of management (1-15). V-AD has a wellestablished role in the management of chronic, large wounds in skin and other soft tissues including the sternum and abdomen, and has been approved by the FDA for this purpose (FDA #). The negative pressure not only helps in effective drainage but also promotes growth of granulation tissue, leading to faster closure of wounds. However, the actual role of V-AD in the management of open chest wounds has not been evaluated in a well-designed prospective trial. To the best of our knowledge, there are currently no data that compares V-AD to traditional open chest wound management techniques. One prospective trial using the mini-VAC with instillation therapy in patients without BPF reported success in 86% of patients (5). Small retrospective cases series and individual case reports have reported varying results with some success noted (1,2,4,6). Reported advantages of using V-AD include decreased frequency of dressing changes and a decrease in the time needed to heal. Pain with application of the V-AD and difficulty in removing the dressings due to impaction have been described as some of the disadvantages (5). A best-evidence review of 23 publications on this topic suggested that V-AD might have some benefits as an adjunct to standard treatments but recommended clinical trials to understand this better (7).

D. SUBJECT INFORMATION

D.1. Target accrual

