A total of 10 patients will be enrolled in the intervention (V-AD) arm of the study. These patients will be recruited from those presenting to Mayo Clinic Florida or Mayo Clinic Rochester with thoracic infections that require surgical intervention. A historic control group of 10 patients with open chest wounds who were treated with the traditional treatment techniques at Mayo Clinic will be selected using propensity-matching methods. We plan to complete our target accrual over a timeframe of approximately 12 months.

D.2. Subject Population

Subjects will be identified by the Principal Investigator or the Co-Investigators. Patients referred for surgical management of thoracic infections, who meet inclusion criteria and none of the exclusion criteria, will be invited to participate in the study. If the subject is interested in more information about

the study, a study coordinator will meet with the patient to discuss further and obtain informed consent.

D.3. Inclusion criteria

- 1. Subject provides informed consent and is:
 - a. >18 years of age,
- 2. Subject is scheduled to undergo surgical intervention(s) as part of the standard care for management of intrathoracic infection.

D.4. Exclusion criteria:

- D.4.1. Patients who have the following conditions will be excluded from participating:
 - 1. Patent bronchopleural fistulas.
 - 2. Severe respiratory failure requiring mechanical ventilation at the time of first consultation.
 - 3. Inability to provide informed consent due to physical or mental impairment.
 - 4. Altered mental status.
 - 5. Proven or suspected malignancy in the wound.
 - 6. Coagulopathy due to medical or pharmacologic reasons.
 - 7. Dependency on anticoagulants or antiplatelet medication due to high risk for adverse events if these medications are stopped for a prolonged period of time.
 - 8. Allergy to acrylic products.
 - 9. Subject is a pregnanat or lactating female

D.4.2. Patients in whom the use of V-AD is determined to be unsafe by the surgeon for any reason will be excluded from the study.

D.5. INITIAL EVALUATION AND INFORMED CONSENT FOR ENROLLMENT

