All patients presenting with an infection in the pleural cavity that requires surgical intervention (exploration, debridement, washout, decortication, etc.), and meet inclusion criteria will be informed about the study by the surgeon prior to the operation. If the initial meeting occurs during regular working hours (8am to 5pm), the study coordinator will review the consent form with the patient and answer any questions that the patient may have about the study. The patient will be reminded that their participation is voluntary, they can withdraw at any time and their care at Mayo Clinic will not be affected whether they choose to participate or not. If the initial consultation is done after regular working hours or on an emergency basis, the surgeon will discuss the availability of the study but will wait till the study coordinator is present to obtain formal consent. In such instances where the patient subsequently consents to being enrolled in the study, the V-AD will not be applied until the next dressing change.

Due to the patient's surgery procedure and other factors patients will be continually assessed for loss or gain or capacity to consent. If it is determined to obtain assent from a patient this will be documented in the patient's medical record. If the patient re-gains capacity to consent, then the patient's consent will at that time be obtained.

E. STUDY DESIGN

E.1. Methods: This will be a prospective pilot study of 10 patients with OCW treated using V-AD at Mayo Clinic in Florida and Rochester.

E.1.2. Procedure for placement of V-AD and subsequent monitoring, including dressing changes.

E.1.2.1. Initial assessment and V-AD application:

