After obtaining informed consent from eligible patients, they will be taken to the operating room for the initial assessment and treatment as determined by the surgeon. The intervention may include, but is not limited to, thoracotomy, minimally invasive thoracic surgery, washout, excisional debridement, pulmonary decortication, pulmonary resection and closure of any obvious bronchopleural fistulas. Aerobic and anaerobic tissue cultures from the infected space will be obtained at the time of surgery. The surgeon will determine if the chest can be closed primarily. If unable to do so due to obvious infection or perceived high risk of developing a subsequent deep space abscess, the surgeon will next assess whether the wound is suitable for management with V-AD (V.A.C.* Therapy, KCI, San Antonio, TX). In the absence of any contraindications, the OCW will then be packed with one or more foam sponges and an airtight transparent dressing. At the time of application, these sponge dressings can be cut to fit within the wound. The type of dressing (black or white foam) to be used will be determined by the surgeon depending on the characteristics of the wound bed. The dressing will then be connected to the negative pressure canister unit and maintained on continuous negative pressure ranging from -75 mmHg to -125 mmHg. Unless otherwise indicated, the dressing will be changed once every 72 hours under IV sedation or anesthesia.

The patient will be admitted to the hospital for at least two supervised dressing changes, at which time the surgeon will re-assess the wound to determine if it can be closed with or without a soft tissue (muscle, omentum, etc.) flap. Wounds determined to be not ready for closure will then be repacked with the V-AD. If no other indication for inpatient hospital care exists other than the V-AD, the patient will be then discharged home or to a skilled nursing facility where the remainder of dressing changes will be performed. If the patient cannot be safely discharged from the hospital, inpatient care will be continued.

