After discharge, the patient will return to the outpatient clinic for wound inspection and dressing change by the surgeon once every two weeks and earlier, if necessary. During hospitalization and clinic visits, a Mayo Clinic photographer or a provider authorized to use the Mayo Clinic imaging software will photograph the wound, which will be a part of the permanent medical record of the patient. At every dressing change in and outside the hospital, the number of individual pieces of foam sponges will be entered in a logbook and accounted for during removal at the next change.

Figure 1: Algorithm for Patient Selection and Enrollment

E.1.2.2. Monitoring:

A prospective database of all patients in the study will be maintained and will record the following:

- a. Name, Medical Record number and Dates of dressing changes
- b. Pain scores visual analogue scores,
- c. Ease of dressing changes (Easy, moderately difficult, very difficult)
- d. Wound bed characteristics including amount of granulation tissue (minimal, moderate and significant) and dimensions (length x breadth x depth in centimeters).
- e. Duration of treatment
- f. Adverse events

E.1.2.3. Discontinuation of V-AD therapy:

1. In the absence of a noticeable improvement in the wound bed after 2 weeks of continuous V-AD therapy, the treatment plan will be re-assessed and the determination will be made as to whether the V-AD therapy should be discontinued.

2. The V-AD will be discontinued if the patient develops severe uncontrolled pain that does not respond to pain medications or a reduction in the negative pressure to -50 mm Hg.

3. In the event of any unpredicted adverse event, such as bleeding, injury to underlying organs, new onset of respiratory distress or allergy to the dressings will result in removing the V-AD.

4. Patients who require treatment with anticoagulation or antiplatelet agents after V-AD application will be removed from the study to avoid hemorrhagic complications.

F. DRUGS/ SUBSTANCES/ DEVICES

The V.A.C. Therapy System has many components that work together to apply negative pressure to wounds. The components include:

- 1. a porous foam dressing which comes in contact with the wound base and equally distributes negative pressure throughout the wound,
- 2. an airtight transparent adhesive drape that covers the foam dressing and
- 3. a software-controlled V.A.C Canister that is connected to the dressing by means of a transparent plastic tubing.

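### Section G has no method for wounds still open at last contact, so the time-to-closure comparison in Aim b can be distorted, in a direction the protocol does not fix

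*Combined protocol and SAP*

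**What the plan says.** **Endpoint.** B.1 hypothesises a shorter time to closure than in a historical cohort. Aim b treats time to closure as the rate of healing and adds: "Time to wound closure further being defined as the total approximation of the wound edges to close the defect". It restricts neither how the edges are brought together nor the date from which time runs. Aim c is separate: "Determine if treatment with V-AD reduces the need for additional procedures to close wounds, such as muscle flaps".

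**Analysis.** Section G includes all 10 V-AD patients and 10 matched controls. It names summary statistics, scatter plots over time with 95% intervals, and visual comparison. It labels the work descriptive and hypothesis generating. It names no censoring rule and no time-to-event method.

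**How long closure takes.** Section C says "these wounds may take months or even years to close by secondary intention". It also says that faster routes are common: "In order to expedite the closure of the wound, additional procedures such as modified Clagett procedure" and thoracoplasty are often used. In E.1.2.1 the surgeon is to "re-assess the wound to determine if it can be closed with or without a soft tissue (muscle, omentum, etc.) flap".

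**How follow-up can end early.** E.1.2.3 item 1 has the treatment plan re-assessed, with V-AD possibly stopped: "In the absence of a noticeable improvement in the wound bed after 2 weeks of continuous V-AD therapy". Items 2 and 3 stop V-AD for pain or adverse events. Item 4 takes patients who come to need anticoagulant or antiplatelet agents out of the study. D.1 says "We plan to complete our target accrual over a timeframe of approximately 12 months". No efficacy cut-off is given, and no follow-up length is given for the controls. The only stated observation window (H.2) is for adverse events; it ends one week after closure or after V-AD ends.

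**The concern.** A time to closure exists only for wounds that have closed. For the others the analyst must choose: enter the last-contact date, enter the stop date, drop the patient, or rank the wound last. Section G leaves that choice open, so it would be made with the data in view. Section G also counts all 10 treated patients while E.1.2.3 item 4 takes some out of the study, and it does not say how both can hold.

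Entering an open wound as though it had closed on the last date seen shortens the apparent time to closure. If the two groups are followed unequally, that creates a difference where none exists. The stopping and removal rules apply only to V-AD patients, which is one reason to expect less complete follow-up there. However, the historical records may also be incomplete, and the protocol does not say.

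Section G says that promising pilot findings will be explored in follow-up studies, so a spurious difference would have consequences even without a test.

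**Working it through.** The plan gives no closure rate, follow-up length or flap rate, so there is no figure of its own to reproduce. The sizes below are illustrations.

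**Assumptions.** No true difference; exponential closure times with median 1, 3 or 6 months; 10 per group. The mean is m = median / ln 2 = 1.443, 4.328 or 8.656 months.

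**1. Early stop entered as a closure time.** Take a stop at 0.5 month (the 2 weeks of E.1.2.3 item 1) for k of 10 V-AD patients.
- A stopped patient contributes on average E[min(T, 0.5)] = m(1 − exp(−0.5/m)) = 0.423, 0.472 or 0.486 months. As a fraction of m this is 0.293, 0.109 or 0.056.
- If the k patients are a random subset, the mean is shortened by (k/10)(1 − that fraction).
- k = 1: 7.1%, 8.9%, 9.4%. k = 2: 14.1%, 17.8%, 18.9%.
- Worst case, the slowest wounds. The largest of 10 exponential times averages (1 + 1/2 + … + 1/10)m = 2.929m, and the second largest 1.929m. Together they are 4.858m of a total of 10m, or 48.6%. Replacing both by 0.5 month shortens the mean by 48.6% − 1/(10m), about 42%, 46% and 47%. For the single slowest, 29.3% − 0.5/(10m) gives about 26%, 28% and 29%.
- A median does not protect here. At a 6-month true median with the two slowest entered at 2 weeks, it is about 3.2 against 6.1 months.

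**2. Data cut-off alone.** Assume uniform accrual over 12 months (D.1), cut-off at month c, controls followed to closure, and open wounds entered at their follow-up time. The mean is shortened by the average of exp(−F/m), where F is follow-up time: (m/12)[exp(−(c − 12)/m) − exp(−c/m)].

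Example, median 6, c = 18: 0.7213 × (0.5 − 0.125) = 0.2705, so 8.66 months reads as 6.31.

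| True median | c = 18 | c = 24 | c = 30 |
|---|---|---|---|
| 6 months | 27.1% | 13.5% | 6.8% |
| 3 months | 8.5% | 2.1% | 0.5% |
| 1 month | at most 0.2% | about 0% | about 0% |

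At a 6-month median, 2.7, 1.35 and 0.67 of 10 wounds are still open at these cut-offs.

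- **Equal follow-up in both groups:** about 0% (simulation, −0.6% to 0.4%).
- **Ordinary median, open wounds entered at follow-up time, true median 6:** in the typical simulated trial, 5.86 against 6.05 months at month 18, or 1 − 5.86/6.05 = about 3%. There is no difference at months 24 and 30. Averaging the median over 200,000 simulated trials instead gives 5.84 against 6.45 at month 18 (about 10%) and under 1% at month 24.
- **Median with open wounds ranked last:** 6.1 months in both groups at month 18.

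**3. Does Kaplan-Meier suffice?** With a 6-month median and cut-off at month 18, the Kaplan-Meier median is 5.2 months in both groups. If the two slowest wounds are censored at the 2-week stop, it is 4.5 instead of the 5.3 obtained by following them to closure. The follow-up rule therefore matters as much as the estimator.

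**The case against.** - **The analysis is only descriptive, and summary statistics could include Kaplan-Meier.** The label removes a test, not a bias: a descriptive mean with open wounds entered as closed is still wrong. No time-to-event method is named, and scatter plots judged by eye supply no rule.
- **The cut-off figures need a mean, slow closure and longer-followed controls.** This stands. Section G does not commit to a mean, and the remark on months or years concerns secondary intention only. Earlier surgical closure, which Aim b allows, would shrink the cut-off bias. The 27% is the unfavourable end of an assumed range.
- **Entering a stop date as closure contradicts Aim b's definition.** It does, and E.1.2.3 item 1 stops a therapy, not follow-up. Only item 4 takes patients out of the study, and nothing suggests that those have the slowest wounds. The 42-47% is therefore a worst case. But the plan does not say what value these patients take instead.
- **A reader might infer that the plan favours V-AD.** The documents do not support this. The early-exit rules act on V-AD patients only, but control follow-up is unstated, so the sign is unknown. Nor does the adverse-event window in H.2 set the end of efficacy follow-up.
- **A reader might infer that the endpoint is invalid because flap closures count.** The documents do not support this either. Closure by any route matches B.1, Aim b defines its own term, and Aim c covers flap use. Differences in flap use or timing can move time to closure either way, but no flap rate is given and no size can be put on it. What remains is that rate of healing is a loose label.

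**Conclusion.** The point holds as an omission in Section G: the named methods do not handle wounds still open, although the protocol makes such wounds foreseeable. The bias shortens apparent closure in whichever group is followed less completely; the net direction cannot be told from the documents.

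Its size rests wholly on the assumptions above:
- about 7-9% of the mean for one random early stop in 10, and 14-19% for two, with 42-47% as the worst case for two;
- about 0% to 27% of a mean from a data cut-off alone, about 4% or less for the median of a typical trial, and about 0% with equal follow-up.

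The change should be made because it is cheap and removes a choice otherwise made at analysis. Confidence is medium, since closure rates and follow-up are unknown. The naming of the endpoint in B.2.b is a minor wording matter.

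**What to change.** In Section G:

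1. Follow every V-AD patient, including those who stop V-AD or are taken out of the study, to closure from the medical record, as far as consent and records allow. Apply the same time origin (date the chest was left open) and the same follow-up rule to the controls.
2. Summarise time to closure by any route with Kaplan-Meier curves and the median with 95% CI per group. Censor at the last date the wound is known to be open, not at the V-AD stop date, and state how many wounds remain open.
3. List for each patient the route of closure (with or without a flap or thoracoplasty) and its date, beside the Aim c proportion. Separate cumulative incidence curves by route are optional with 10 per group.
4. Keep the descriptive, hypothesis-generating label. In B.2.b, preferably call the endpoint time to closure by any route.

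**Cost.** A few sentences, plus closure date and route read from the record in both groups. Intervals will be wide: at an assumed 6-month median, a typical 95% CI for the V-AD median is 0.6 to 11.7 months at month 24. The upper limit is not reached in 44%, 13% and 3% of simulated trials at months 18, 24 and 30.

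With the common origin, the wait for patients consented after hours, for whom "the V-AD will not be applied until the next dressing change" (D.5), counts in V-AD time. An assumed 3 days is about 10%, 3% or 2% of a 1-, 3- or 6-month median, so report it. No clinical change is proposed.

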There are 2 types of foam dressings that will be used in the study:

- 1. An open pore reticulated polyurethane foam (V.A.C Granufoam Dressing)
- 2. A polyvinyl alcohol foam (V.A.C WhiteFoam Dressing).

The canister system is self-monitoring and can be set to different therapy modes (continuous or intermittent) depending on the individual patient and wound needs. In-built alarm systems can detect a loss of pressure or tubing blockage, alerting the care team to troubleshoot these issues.

G. DATA ANALYSIS

Exploratory analysis will be used to analyze the correlative studies comparing the healing rates. The analysis will include all 10 patients treated with V-AD and a matched group of 10 patients previously treated for empyema at Mayo Clinic. Due to the limited sample size the analysis will be descriptive and hypothesis generating. Any information that shows promise based on the pilot data will be explored in follow-up studies. Descriptive statistics, and scatter plots with 95% confidence intervals will graphed over time. Data will be visually inspected for differences.

The following datasets will be compared during analysis:

1. V-AD treated patients versus historical controls.

H. RISKS

H.1. Potential risks: The specific risks of V-AD use in the chest cavity have been reported and include pain, hypotension and difficulty in removing the sponge (11). No serious adverse events have been reported to date. General risks of NPWT when applied to other parts of the body include suction injury to skin and injury to underlying organs such as bowel or blood vessels. Extrapolating these adverse effects to the chest, there is an unquantifiable risk of injury to intrathoracic organs – lungs, heart, large vessels (aorta, pulmonary artery or veins). Hypothetically, injury to the lungs can lead to worsening of bronchopleural fistulas, air leaks or pulmonary hemorrhage; injury to the vascular structures can lead to significant hemorrhage, and even death. During removal of the black foam sponge dressing, it is possible to cause injury to the underlying structures due to excessive traction or adherence from tissue ingrowth.

H 1.1. Potential Severe Adverse Events

- Death
- Respiratory failure requiring ventilation (for any cause)
- Major cardiac arrhythmias requiring cardioversion or hospitalization which are hemodynamically significant.
- Massive Hemoptysis (life-threatening or requiring an intervention e.g. embolization)

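### The historical controls are to be chosen by a propensity match whose timing, operator and specification are not fixed, and nothing keeps that choice blind to outcome

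*Combined protocol and SAP*

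**What the plan says.** Section D.1 sets the size of both groups: "A total of 10 patients will be enrolled in the intervention (V-AD) arm of the study", and "A historic control group of 10 patients with open chest wounds who were treated with the traditional treatment techniques", who "will be selected using propensity-matching methods". Section G repeats that a matched group will be compared, but describes it as "a matched group of 10 patients previously treated for empyema at Mayo Clinic". These two places are the whole description of control selection.

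The outcome and the expected direction are stated. Aim b in B.2 is to "Compare the rate of healing (time-to closure) of OCW in patients treated with V-AD to a historical cohort", and the hypothesis in B.1 is that V-AD "will decrease the time-to-closure of such wounds when compared to a historical cohort of patients managed by traditional wound care management". Aim c adds the need for further closing procedures such as muscle flaps. Section G lists a single comparison, V-AD against historical controls. It plans descriptive statistics, plots and visual inspection, with no formal test.

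The only timing given is for enrolment: "We plan to complete our target accrual over a timeframe of approximately 12 months". No date or stage is given for the match.

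**The concern.** Propensity matching is a family of procedures. The candidate pool, calendar period, covariates, algorithm, caliper and matching order all have to be chosen. Several choices would be defensible, and each can return a different set of 10 controls. Here even the pool is unsettled, because D.1 speaks of open chest wounds and Section G of empyema.

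The controls are historical, so their closure times and flap procedures generally exist before anyone matches. A propensity score also needs the V-AD patients' baseline data, so the match cannot be completed before those patients are enrolled. By then some or all of their closure results may be known. The surgeon re-examines each wound under E.1.2.1, so V-AD results are not masked.

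Freedom of choice, visible outcomes and a hypothesis with a stated direction are together enough for selection bias, and it need not be deliberate. Knowing the control outcomes alone suffices. At stake is the study's one listed comparison, which is judged by eye and in which 10 controls carry the whole reference group.

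**Working it through.** **The plan's own figure.** There is none to reproduce. The documents give no effect size, SD, power or pool size, and the 10 + 10 is stated without derivation.

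**Inputs from the documents.** 10 V-AD patients and 10 controls (D.1), hence 1:1 matching; outcome time to closure (B.2, aim b); direction favouring V-AD (B.1).

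**Assumed inputs.** Candidate pool of 10 to 80; number of matches tried, 3 to 10; six baseline covariates, of which two are prognostic (weights 0.6 and 0.4); log closure time scaled to SD 1; no true treatment effect.

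**Chance benchmark.** For two unmatched groups of 10, the standard error of the difference in means is √(1/10 + 1/10) = 0.447 SD. The chance of V-AD looking better by more than 0.5 SD is then P(Z > 0.5/0.447) = P(Z > 1.12) ≈ 13%. Matching on prognostic covariates lowers this somewhat, which agrees with the simulated 9 to 10% for one fixed match at pool 40.

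**Simulation 1.** Optimal 1:1 matching on random subsets of 2 to 4 covariates. The analyst either takes one match fixed in advance or keeps the most favourable of several. Where two values are shown, they come from repeated runs.

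| Pool | Matches tried | Mean bias toward V-AD (SD) | Chance of > 0.5 SD | Same chance, one fixed match |
|---|---|---|---|---|
| 10 | 5 | about 0 (no choice exists) | – | – |
| 12 | 5 | 0.11 to 0.14 | 18% | 12% |
| 15 | 5 | 0.18 | 22% | 11% |
| 40 | 3 | 0.20 | 21% | 9 to 10% |
| 40 | 5 | 0.26 to 0.27 | 23 to 26% | 9 to 10% |
| 40 | 10 | 0.35 | 33% | 9 to 10% |
| 20 to 80 | 3 to 10 | 0.16 to 0.40 | 18 to 37% | – |

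Mean bias for one match fixed in advance is 0 within simulation error.

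**In units of time.** With an assumed log-time SD of 0.8, a bias of 0.27 SD is exp(0.27 × 0.8) = exp(0.216) = 1.24. Control closure times would look about 24% longer with no effect present.

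**Simulation 2, a different model.** Logistic propensity score, greedy nearest-neighbour matching, and six covariates that together explain 30% of the variance of log time. The result is the control/V-AD ratio of geometric mean closure times.

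| Pool | Log-SD | One fixed match | Best of 5 | Best of 5 in SD units |
|---|---|---|---|---|
| 20 | 1.0 | 1.01 | 1.29 | ln 1.29 = 0.25 |
| 40 | 1.0 | 0.99 | 1.36 | ln 1.36 = 0.31 |
| 80 | 1.0 | 1.00 | 1.42 | ln 1.42 = 0.35 |
| 40 | 0.6 | 1.00 | 1.21 | ln 1.21 / 0.6 = 0.32 |

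The two models use different matching methods and agree on direction and approximate size.

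**The case against.** **The figures assume a behaviour.** They apply only if several matches are tried and the favourable one is kept. Nothing in the documents shows that this will happen, and with one match the bias is zero. This stands. The figures show how large the exposure is; they do not predict the result.

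**The pool may be small.** Eligible controls need an open chest wound. If the trial's exclusions in D.4 are applied to them, they also need to be free of patent fistula, malignancy in the wound and dependency on anticoagulants. A pool little larger than 10 is plausible, and there the bias shrinks or vanishes. This also stands, so the range has no lower floor above zero.

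**The analysis is only descriptive.** Section G says its purpose is to generate hypotheses, and no test is planned. This limits the consequence but does not remove it. Section H.2 names efficacy as the primary endpoint, and a descriptive label does not correct a biased estimate.

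**Stronger readings that the documents do not support.** A reader might infer that outcomes in both groups will already be known when the controls are picked. The documents give no timing, and the match could be made at the end of accrual while V-AD wounds are still open. A reader might also infer that the surgeons who treated the controls make the match; D.1 says only that controls were treated at the same institution. Nor is it right that such a bias could never be detected, because a result under an alternative match would show dependence on the choice.

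**Conclusion.** The concern holds in this form: the timing, operator and specification of the match are not fixed, control outcomes are already on record, V-AD outcomes may be, and nothing keeps the selection blind to either. An outcome-aware choice could produce an apparent V-AD benefit where none exists.

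Under the assumptions above, the size runs from nothing at a pool of 10, through about 0.1 to 0.2 SD at 12 to 15, to about 0.16 to 0.40 SD at 20 to 80. Pool size, SD, covariate strength and number of matches tried are all assumptions, so the sizes are illustrative. The direction does not depend on them, provided there is some choice of controls and the favourable match is preferred. The documents give no evidence that outcome-driven selection is intended. This should be corrected before any matching begins, because blindness to outcome cannot be restored afterwards.

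**What to change.** Add to D.1:

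> Candidate controls are identified by stated eligibility criteria and calendar period. The statistician receives eligibility and baseline variables only (no closure date, flap, treatment duration or complications), fixes the covariates, method and caliper, and date-stamps the control list before control outcomes are abstracted or merged with V-AD outcomes.

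State the eligibility criteria and period in the protocol itself, and use one description of the pool in D.1 and Section G. Otherwise selection can enter while the candidate list is being assembled, before the baseline-only file exists. In Section G, name one alternative match in advance and report its result as a sensitivity analysis.

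The cost is that charts are abstracted in two steps, baseline first and outcomes after the list is locked. Existing staff can do this. It needs no extra patients and changes nothing in patient care.
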